13.2. Assessing Adverse Events

In conjunction with the medical monitor, the Investigator will evaluate adverse events to ensure the events are categorized correctly. Elements of categorization will include:

- Seriousness/Classifications (see definition in Section 13.1)
- Causality or Relatedness – i.e. the relationship between the test article, study treatment or study procedures and the adverse event (not related; unlikely related; possibly related; related - see definition in Section 13.2.1)
- Adverse Event Severity – Adverse event severity is used to assess the degree of intensity of the adverse event (mild; moderate; severe for all events - see definition in Section 0)
- Outcome – not recovered or not resolved; recovering or resolving; recovered or resolved with sequelae; recovered or resolved; death related to adverse event; unknown

- Actions Taken – none; temporarily discontinued; permanently discontinued; other

13.2.1. Causality Assessment

Causality Assessment – A determination of the relationship between an adverse event and the test article. The test article relationship for each adverse event should be determined by the investigator using these explanations:

- Not Related- An adverse event that is not related to the use of the test article, study treatment or study procedures
- Unlikely Related – An adverse event for which an alternative explanation is more likely, e.g. concomitant treatment, concomitant disease(s), or the relationship of time suggests that a causal relationship is not likely
- Possibly Related – An adverse event that might be due to the use of the test article, or to the study treatment or study procedures. An alternative explanation, e.g. concomitant treatment, concomitant disease(s), is inconclusive. The relationship in time is reasonable. Therefore, the causal relationship cannot be excluded
- Related – An adverse event that is listed as a possible adverse effect (device) or adverse reaction (drug) and cannot be reasonably explained by an alternative explanation, e.g. concomitant treatment of concomitant disease(s). The relationship in time is very suggestive, e.g. it is confirmed by de-challenge and re-challenge

13.2.2. Severity Assessment

Severity Assessment – A qualitative assessment of the degree of intensity of an adverse event as determined by the Investigator or reported to him/her by the subject. The assessment of severity is made irrespective of test article, study treatment or study procedure relationship or seriousness of the event and should be evaluated according to the following scale:

- Mild – Event is noticeable to the subject, but is easily tolerated and does not interfere with the subject's daily activities
- Moderate – Event is bothersome, possible requiring additional therapy, and may interfere with the subject's daily activities
- Severe – Event is intolerable, necessitates additional therapy or alteration of therapy and interferes with the subject's daily activities

13.3. Documentation and Follow-Up of Adverse Events

The recording and documenting of adverse events (ocular and non-ocular) begins when the subjects are exposed to the test article, study treatment or study procedure. Adverse events reported before the use of test article, start of study treatment, or study procedures will be recorded as medical history. However, if the condition deteriorates at any time during the study it will be recorded and reported as an AE. Untoward medical events reported after the subject's exit from the study will be recorded as adverse events at the discretion of the Investigator.

Upon finding an adverse event, the Principal Investigator will document the condition in the subject record and in the eCRFs. He/she will complete the Adverse Event /eCRF.

Complete descriptions of all adverse events must be available in the subject record. All Adverse Events including local and systemic reactions not meeting the criteria for “serious adverse events” shall be captured on the appropriate case report form or electronic data system. All adverse events occurring while the subject is enrolled in the study must be documented appropriately regardless of relationship.

It is the Investigator’s responsibility to maintain documentation of each reported adverse event. All adverse events will be followed in accordance with applicable licensing requirements. Such documentation will include the following:

- Adverse event (diagnosis not symptom)
- Drawings or photographs (where appropriate) that detail the finding (e.g., size, location, and depth, etc.)
- Date the clinical site was notified
- Date and time of onset
- Date and time of resolution
- Adverse event classification, severity, and relationship to test articles, as applicable
- Treatment regimen instituted, including concomitant medications prescribed, in accordance with applicable licensing requirements
- Any referral to another health care provider if needed
- Outcome, ocular damage (if any)
- Likely etiology
- Best corrected visual acuity at the discovery of the event and upon conclusion of the event

In addition, if an infiltrate(s) is present, he/she will complete the Corneal Infiltrate Assessment eCRF. Where necessary, a culture of the corneal lesion will be collected to determine if the infection is microbial in nature. If cultures are collected, the date of culture collection and laboratory utilized will be recorded.

Changes in the severity of an AE shall be documented to allow an assessment of the duration of the event at each level of intensity to be performed. Adverse events characterized as intermittent require documentation of the onset and duration of each episode. Changes in the assessment of relationship to the Test Article shall also be clearly documented.

Subjects who present with an adverse event shall be followed by the Investigator, within licensure, until all signs and symptoms have returned to pre-treatment status, stabilized, or been satisfactorily resolved. If further treatment beyond licensure is required, the patient will be referred to the appropriate health care provider. The Investigator will use his/her clinical judgment as to whether a subject reporting with an adverse event will continue in the study. If a subject is discontinued from the study, it will be the responsibility of the Investigator to record the reason for discontinuation. The Investigator will also document the adverse event appropriately and complete the Adverse Event eCRF. Any subjects with ongoing adverse events related to the test article, study treatment or study procedures, as of the final study visit date, should be followed to resolution of the adverse event or until referral to an appropriate health care provider, as recommended by the Investigator.

Non-ocular adverse events that are not related to the test article, study treatment, or study procedures may be recorded as “ongoing” without further follow-up.

13.4. Reporting Adverse Events

The Investigator will notify the Sponsor of an adverse event by e-mail, facsimile, or telephone as soon as possible and no later than 24 hours from discovery for any serious /significant adverse events, and 2 days from discovery for any non-significant adverse event. In addition, a written report will be submitted by the Principal Investigator to the IEC/IRB according to their requirements (Section 13.4.2). The report will comment whether the adverse event was considered to be related to the test article, study treatment or study procedures.

13.4.1. Reporting Adverse Events to Sponsor

Serious/Significant Adverse Events

The Investigator will inform the sponsor of all serious/significant adverse events occurring during the study period as soon as possible by e-mail, fax, or telephone, but no later than 24 hours following discovery of the event. The Investigator is obligated to pursue and obtain information requested by the Sponsor in addition to that information reported on the eCRF. All subjects experiencing a serious/significant adverse event must be followed up and all outcomes must be reported.

When medically necessary, the Investigator may break the randomization code to determine the identity of the treatment that the subject received. The Sponsor and study monitor should be notified prior to unmasking the test articles.

In the event of a serious/significant adverse event, the Investigator must:

- Notify the Sponsor immediately
- Obtain and maintain in the subject’s records all pertinent medical information and medical judgment for colleagues who assisted in the treatment and follow-up of the subject
- Provide the Sponsor with a complete case history which includes a statement as to whether the event was or was not related to the use of the test article
- Notify the IEC/IRB as required by the IEC/IRB reporting procedure according to national regulations

Unanticipated (Serious) Adverse Device Effect (UADE)

In the event of an Unanticipated (Serious) Adverse Device Effect (UADE), the Investigator will submit a report of the UADE to the Sponsor and IEC/IRB as soon as possible, but no later than 24 hours after the Investigator first learns of the effect. This report is in addition to the immediate notification mentioned above.

The Sponsor must conduct an evaluation of the UADE and must report the results of the evaluation to FDA, the IEC/IRB and participating Investigators within 10 working days after the Sponsor first receives notification of the effect.

Non-Serious Adverse Events

All non-serious adverse events, including non-serious adverse device effects, will be reported to the sponsor by the Investigator no later than 2 days from discovery.

13.4.2. Reporting Adverse Events to the Responsible IEC/IRB and Health Authorities

Adverse events that meet the IEC/IRB requirements for reporting must be reported within the IEC/IRB's written guidelines. Each clinical site will refer to and follow any guidelines set forth by their Approving IEC/IRB. Each clinical site will refer to and follow any guidelines set forth by their local governing Health Authorities.

The Sponsor will report applicable Adverse Events to the local health authorities according the written guidelines, including reporting timelines.

13.4.3. Event of Special Interest

None

13.5. Reporting of Pregnancy

Subjects reporting pregnancy (by self-report) during the study will be discontinued after the event is recorded as an Adverse Event. Once discontinued, pregnant participants and their fetuses will not be monitored for study related purposes. At the Investigator's discretion, the study participant may be followed by the Investigator through delivery. However, this data will not be collected as part of the clinical study database. Pregnant participants are not discontinued from contact lens or solution related studies for safety concerns, but due to general concerns relating to pregnancy and contact lens use. Specifically, pregnant women are discontinued due to fluctuations in refractive error and/or visual acuity that occur secondary to systemic hormonal changes, and not due to unforeseen health risks to the mother or fetus.

14. STATISTICAL METHODS

14.1. General Considerations

All data summaries and statistical analyses will be performed using the Statistical Analysis System (SAS) software Version 9.4 (SAS Institute, Cary, NC). Throughout the analysis of data, the results for each subject/eye will be used when available for summarization and statistical analysis. Unscheduled visits will be summarized separately and will be excluded from the statistical analysis.

Summary tables (Descriptive statistics and/or frequency tables) will be provided for all baseline variables, efficacy variables and safety variables as appropriate. Continuous variables will be summarized with descriptive statistics (n, mean, standard deviation [SD], median, minimum and maximum). Frequency count and percentage of subjects or eyes within each category will be provided for categorical data.

Summaries will be presented by study lens type and will be performed separately by completion status (Safety Population or Per-Protocol Population). All analyses will be conducted on per-protocol population (see Section 14.3).

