3.10	Lens Fit Assessment:	
Evaluate and grade lens centration, primary gaze movement, upgaze movement and tightness (push-up test).
 
 • The subject should not proceed to wear the lenses if any of the following is observed: • presence of limbal exposure (appearance of clear cornea) in any gaze • presence of edge lift • presence of unacceptable movement 	

		
(excessive or insufficient) in all three movement categories (primary gaze, upgaze, and push-up).
 
If either lens is deemed unacceptable, the subject will be discontinued from the study. Remove the lenses, perform a slit-lamp evaluation, and complete the Final Evaluation form.
	
3.11	Collection of unworn lenses (if applicable)	
If the first lens type fit on the subject was the daily disposable lenses collect unworn lenses returned by the subject.
	
3.12	Lens Removal	
Have the subject remove the study lenses and store in saline in a labeled glass vial.
 
Note: Lenses do not need to be stored in a refrigerator.
	
3.13	Biomicroscopy	
Perform biomicroscopy OD and OS. Slit Lamp Classification Scales will be used to grade the findings.
 
For the conjunctival redness [REDACTED] 0.5 unit increments will be used in the grading.
 
Corneal Staining Assessment [REDACTED] will be graded in 1.0 increments.
 
If the clearance of the fluorescein needs to be expedited, preservative-free rewetting drops or saline may be instilled.
	[REDACTED] [REDACTED] [REDACTED]
3.14	Distance and Near Exit Visual Acuity	
Distance and near Snellen visual acuity will be measured for each eye with the subject's habitual correction in place.
 
For near measures use the ETDRS 2000 Series Chart 1 or 2. The acuity will be recorded to the nearest letter OD, OS and OU.
	[REDACTED]
3.15	Schedule Follow-up	
The subject will be scheduled to return for their next appointment in 7 ± 3 days.
 
NOTE: Subject may wear their habitual spectacles or contact lenses during the washout period.
	

VISIT 4

The subjects may present to Visit 4 wearing their habitual spectacles or contact lenses, if required for their distance vision.

Visit 4: Baseline Treatment 2		
Step	Procedure	Details
4.1	Adverse Events and Concomitant Medications Review	
Review the subject's concomitant medications and record any changes from the previous study visit.
 
Record any adverse events or medical history changes from the previous study visit.

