6.11	Collection of unworn lenses (if applicable)	If the second lens type fit on the subject was the daily disposable lenses collect unworn lenses returned by the subject.	
6.12	Lens Removal	Have the subject remove the study lenses and store in saline in a labeled glass vial. NOTE: Lenses do not need to be stored in a refrigerator.	
6.13	Biomicroscopy	Perform biomicroscopy OD and OS. Slit Lamp Classification Scales will be used to grade the findings. For the conjunctival redness [REDACTED] 0.5 unit increments will be used in the grading. Corneal Staining Assessment [REDACTED] will be graded in 1.0 increments. If the clearance of the fluorescein needs to be expedited, preservative-free rewetting drops may be instilled.	[REDACTED] [REDACTED] [REDACTED]

FINAL EVALUATION

The final evaluation will ordinarily take place immediately following the last scheduled follow-up visit per the study protocol. It may also take place at any point the subject discontinues the study or is terminated from the study.

Final Evaluation			
Step	Procedure	Details	CTP
F.1	Final Exam Form	Indicate if the subject completed the study successfully. If subject discontinued from the study, indicate the reason.	
F.2	Subjective spherocylindrical Refraction	Perform bare-eye subjective spherocylindrical refraction with a phoropter and record the best corrected distance visual acuity to the nearest letter (OD, OS, and OU).	[REDACTED] [REDACTED]
F.3	Exit Slit Lamp Biomicroscopy	FDA Slit Lamp Classification Scale will be used to grade the findings and determine eligibility. If the clearance of the fluorescein needs to be expedited, preservative-free rewetting drops or saline may be instilled.	[REDACTED]

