8. SUBJECTS COMPLETION/WITHDRAWAL

8.1. Completion Criteria

Subjects are considered to have completed the study if they:

- provided informed consent
- they are eligible
- completed all study visits

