8.2. Withdrawal/Discontinuation from the Study

A subject will be withdrawn from the study for any of the following reasons:

- Subject death during the study period
- Subject withdrawal of consent
- Subject not compliant to protocol
- Subject lost to follow-up
- Subject no longer meets eligibility criteria (e.g. the subject becomes pregnant)
- Subject develops significant or serious adverse events causing discontinuation of study lens wear
- Subjects who have experienced a Corneal Infiltrative Event (CIE)
- Investigator's clinical judgment regarding the subject safety reasons (that it is in the best interest of the subject to stop treatment)
- Subject missed two consecutive study visits
- Subject not compliant with study lens wear schedule
- Subject not successfully dispensed due to lack of efficacy and safety including poor vision, poor comfort or unacceptable fit

For discontinued subjects, the Investigator will:

- Complete the current visit (scheduled or unscheduled)
- Complete the Final Evaluation, indicating the reason that the subject was discontinued from the study
- Record the spherocylindrical refraction with best corrected distance visual acuity
- Collect used test article(s) (worn or brought to the visit) from the subject and discard them, unless otherwise stated in Section 6.7
- Collect all unused test article(s) from the subject

An additional subject may be enrolled if a subject discontinues from the study prematurely.

In cases where a subject is lost to follow-up, every possible effort must be made to contact the subject and determine the reason for discontinuation/withdrawal. The measures taken to follow up must be documented including two written attempts and a certified letter (or equivalent) as the final attempt.

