14.3. Analysis Populations

Safety Population:

All subjects who were administered any test article excluding subjects who drop out prior to administering any test article. At least one observation should be recorded.

Per-Protocol Population:

All subjects who have successfully completed all visits and did not substantially deviate from the protocol as determined by the trial cohort review committee prior to database hard lock (Per-Protocol Population). Justification of excluding subjects with protocol deviations in the Per-Protocol Population set will be documented in a memo to file.

Intent-to-Treat (ITT) Population:

All subjects regardless of actual treatment and subsequent withdrawal from study or deviation from protocol. At least one observation should be recorded.

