14.5. Primary Analysis

Primary efficacy analysis:

The lens centration and lens movement outcomes will be converted to a binary response where 1= lens is centered or have optimal lens movement, and 0=otherwise.

The proportion of response ("1") will be analyzed using a generalized linear mixed model with a binary distribution and logit link function for all questions. Each model will include the experimental design factors: lens, period and lens by period interaction as fixed effects; and site and subject nested in site as random effects. Other baseline characteristics known to be important such as subject group (myope/hyperope), age, gender, and/or add power will be included as fixed covariates when appropriate. The covariance between residual errors from two eyes from the same subject at the same lens wearing period will be selected based on the finite-sample corrected Akaike's Information Criterion.⁶ Covariance structures considered may include: Homogenous compound symmetry (CS) and Unstructured covariance structure (UN). The structure that returns the lowest Akaike Information Criteria Corrected (AICC) will be selected as the structure that best fit the data.

Comparisons between the study lenses will be carried out using two-sided 95% confidence intervals of odds ratios (odds ratio calculated as Test / Control) for each individual question. Non-inferiority will be concluded if the lower limit is above 0.67. Superiority will be concluded if the lower limit is above 1.0.

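### Per-Protocol-only analysis drops a recorded Visit 3 movement failure from the primary model because of the failure itself, and no ITT analysis stands beside it

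*Combined protocol and SAP*

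**What the plan says.** Section 14.1: "All analyses will be conducted on per-protocol population (see Section 14.3". Section 14.3 defines that population as "All subjects who have successfully completed all visits and did not substantially deviate from the protocol". Section 14.3 also defines an ITT set that ignores withdrawal, but no analysis is assigned to it. Section 14.1 adds summary tables for the Safety Population.

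Section 2.3 places both primary endpoints after 6-8 days in the optimized lenses. That is Visit 3 in Period 1 and Visit 6 in Period 2. Section 14.5 codes each eye as "1= lens is centered or have optimal lens movement, and 0=otherwise".

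Step 3.10 grades fit at Visit 3 and lists grounds for stopping wear: limbal exposure, edge lift, or unacceptable movement in all three "movement categories (primary gaze, upgaze, and push-up"). It continues: "If either lens is deemed unacceptable, the subject will be discontinued from the study". Step 6.10 repeats this at Visit 6.

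Section 8.1 asks of a completer only consent, eligibility and that they "completed all study visits". Step F.1 reads "Indicate if the subject completed the study successfully. If subject discontinued from the study, indicate the reason". Section 8.2 allows replacement: "An additional subject may be enrolled if a subject discontinues from the study prematurely".

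**The concern.** This is not ordinary missing data. At Visit 3 the endpoint is observed, and the subject is then removed because of what was observed. Primary-gaze movement is both the primary endpoint and one of the three grounds that together trigger discontinuation, so membership of the analysis set depends on the outcome.

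A fit discontinuation at Visit 4 or 5 also discards valid Period 1 grades on the other lens. Replacement means that subjects who did not fit can be exchanged for subjects who do.

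Section 14.2 calls this a pilot whose data will be used to design later trials. What is at stake is a movement estimate that leaves out the worst fits, possibly unequally by lens, and a non-inferiority statement that rests on that estimate alone.

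**Working it through.** **1. The rule chain.**

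| Rule | Where | Consequence |
|---|---|---|
| Movement unacceptable in all three categories | Step 3.10 | Primary-gaze movement is not optimal |
| Not optimal | 14.5 | Recorded score 0 |
| Either lens unacceptable | Step 3.10 | Subject discontinued; no Visits 4-6 |
| All visits required | 14.3 | Subject not Per-Protocol |
| All analyses on Per-Protocol | 14.1 | Recorded 0 leaves the model, with the fellow eye and the centration grades |

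The lens-fitting procedure in Appendix I is redacted. A visible example label there marks a minimal movement grade of -1 as acceptable, so acceptable is wider than optimal and an unacceptable grade cannot be optimal. A primary-gaze failure alone does not trigger the rule and stays in the model.

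**2. Effect on the movement odds ratio.** Inputs from the documents: Control proportion 0.75 (14.2) and margin 0.67 (14.5). Assumed: true OR equal to 0.67; half of each lens's eyes graded at Visit 3 (two sequences, 5.1); eyes independent; a share q of failures at discontinuation level; Visit 6 failures kept.

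- Control odds = 0.75/0.25 = 3. Test odds = 0.67 × 3 = 2.01, so Test success = 2.01/3.01 = 0.668 and failure = 0.332.
- Deleting a share q of Test failures in Period 1 only gives Test odds = 2.01 × 2/(2 − q).
- q = 20%: 2.01 × 2/1.8 = 2.233; OR = 2.233/3 = **0.74**.
- q = 40%: 2.01 × 2/1.6 = 2.513; OR = 2.513/3 = **0.84**.
- Reverse case, Control failures only: Control odds = 3 × 2/(2 − q) = 3.333 or 3.75; OR = 2.01/3.333 = 0.60 or 2.01/3.75 = 0.54.
- Equal shares, q = 40% on both lenses. Discontinued subjects also drop out of Period 2, so the Test factor is (2 − 0.25q)/(2 − q − 0.25q) = 1.9/1.5 and the Control factor is (2 − 0.332q)/(2 − q − 0.332q) = 1.867/1.467. OR = (2.01 × 1.267)/(3 × 1.273) = **0.67**.

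**3. The same effect in counts.** Assume 50 subjects, 67 of 100 Test eyes optimal and Control at 75%: OR = (67/33)/3 = 0.68. Deleting k Test subjects who failed in both eyes at Visit 3 gives [67/(33 − 2k)]/3, which is 0.72 for k = 1 and 0.97 for k = 5. If only one eye fails and its optimal fellow eye goes too, [(67 − k)/(33 − k)]/3 gives 0.69 and 0.74.

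**4. Centration.** The fitting guides in Appendices G and H list good centration among the features of a tight lens with little or no movement. A deleted centration grade can therefore be 0 or 1. If centration is unrelated to the movement failure, its odds ratio is not biased.

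**5. Earlier discontinuations.** A misfit at Visit 1, 2, 4 or 5 leaves no endpoint grade for that lens, so neither Per-Protocol nor a recorded-grades analysis contains it. Assume per-eye misfit of 10% Test and 2% Control, all before the endpoint visit. With independent eyes both analyses give [0.668/(0.332 − 0.10)]/[0.75/(0.25 − 0.02)] = 2.88/3.26 = 0.88. A simulation at those rates (50 subjects, within-subject latent correlation 0.3 and 0.5, mixed logistic model without site or covariates) gave:

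- Per-Protocol: 0.83-0.86
- recorded grades only: 0.93-0.94
- misfitting eye scored 0, fellow eye at its last grade: 0.63-0.66
- both eyes scored 0: 0.54

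**The case against.** **Per-Protocol is a usual set for non-inferiority.** True, and a reason to keep it. It does not answer the point that membership here depends on the endpoint and nothing stands beside it.

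**The Safety Population tables will show the deleted grades.** They should, by lens, and that is useful for designing a later trial. They are descriptive and give no adjusted odds ratio or confidence interval.

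**Section 14.9 already provides multiple imputation for dropout.** The planned loss from 50 to 40 is 10/50 = 20%, above the 15% trigger, so it may well run. But it is conditional and its population is not stated. Read with 14.1, it would run on a set that contains no dropouts. It also fills missing values and does not restore observed ones.

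**Such failures may be rare.** This stands. Lenses reaching Visit 3 have passed the same criteria at steps 1.27 and 2.10. In the simulation, assumed per-eye rates of 3% Test and 1% Control left the Per-Protocol odds ratio at 0.67-0.70.

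**ITT should replace Per-Protocol as primary.** A reader might infer this, but the material does not support it. For losses before the endpoint visit, recorded grades alone can be further from the truth than Per-Protocol (step 5). Scoring those losses 0 answers a different question from the endpoint in Section 2.3.

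**Conclusion.** The point holds as a gap in the analysis plan. A discontinuation-level movement failure at Visit 3 is recorded and then excluded from the primary movement model because of its own value, and no inferential analysis retains it.

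The movement odds ratio is biased only if the discontinuation-level share of failures differs by lens. The figures of 0.74 and 0.84 rest on assumed shares of 20% and 40% for Test and none for Control. Equal shares give about 0.67, and the reverse imbalance moves the estimate against Test.

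A reader might infer that the plan favours the Test lens, or that its non-inferiority error rate is materially inflated. The documents give no misfit rates, so neither follows. Nor does it follow that centration is biased.

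Whether the same failure at Visit 6 stays in is unsettled: Section 8.1 would keep it, while step 6.10 and the wording of F.1 and 14.3 could exclude it. The mechanism is certain and its size unknown, so a supportive analysis is warranted rather than a new primary set.

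**What to change.** Keep the Per-Protocol analysis and make these additions to Section 14:

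- Report beside it the same centration and movement models on the ITT set already defined in 14.3, using every recorded Visit 3 and Visit 6 grade.
- Add one movement sensitivity analysis. An eye discontinued for movement before the endpoint visit scores 0 for that lens, and the fellow eye keeps its last recorded grade. Label it as a different question from the endpoint after 6-8 days in the optimized lenses. Do not give centration an automatic 0.
- Describe non-inferiority as robust only if the Per-Protocol and ITT results agree, with the sensitivity result shown alongside.
- Tabulate fit discontinuations by lens, visit and reason.
- State whether a Visit 6 misfit counts as successful completion of all visits, and that the 14.9 imputation uses the ITT set.

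Step 4.13 treats excessive movement in primary and up gaze as unacceptable, while the other fit steps require all three categories. These passages must be reconciled. No change to the clinical discontinuation rule is proposed.

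The cost is analysis work and reporting, with no new data. A non-inferiority statement may be slightly harder to support.
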